9.2. Analyses Sets

The populations are defined in the CPMP Master Protocol.

The PK population includes all randomized participants who received a dose of LY3526318 at Visit 3 and have at least 1 evaluable PK sample collected.

9.3. Statistical Analyses

Any change to the data analysis methods described in this ISA will require an amendment only if it changes a principal feature of the ISA. Any other change to the data analysis methods described, and the justification for making the change, will be described in the statistical analysis plan (SAP) and the clinical study report. Additional exploratory analyses of the data will be conducted as deemed appropriate.

The ISA SAP will be finalized prior to unblinding, and it will include more technical and detailed descriptions of the statistical analyses described in this section.

9.3.1. General Considerations

The primary endpoint and analyses have been described in the CPMP Master Protocol.

Any borrowing of placebo or treatment effect information will be specified in the ISA SAP. Secondary and tertiary/exploratory endpoints and analyses are described in the CPMP Master Protocol and CLBP DSA CPMP(2).

9.3.2. Exploratory Endpoint Analysis

Exploratory analyses may be described in the ISA SAP.

9.3.3. Safety Analyses

Safety analyses have been described in the CPMP Master Protocol. Additional ISA specific safety analyses may be described in the ISA SAP.

9.3.4. Other Analyses

9.3.4.1. Pharmacokinetic and Pharmacodynamic Analyses

The observed plasma concentrations for LY3526318 will be reported graphically and descriptively.

Pharmacokinetic modeling and exposure-response analyses of efficacy measures may be conducted. If conducted, the analyses will be performed using population analysis software, NONMEM[®], if data allows. The version of any software used for the analysis will be documented, and the program will meet the Lilly requirements of software validation. It is possible that other validated, equivalent PK software programs may be used if appropriate, warranted, and approved by Global PK/pharmacodynamic management. Data may be pooled with data from other studies for an integrated PK and/or PK/pharmacodynamic analysis.

A limited number of pre-identified individuals independent of the study team may receive access to unblinded data, as specified in the unblinding plan, prior to the interim or final database lock, in order to initiate the final population PK and/or exposure-response model development processes. Information that may unblind the study during the analyses will not be reported to study sites or the blinded study team until the study has been unblinded.

9.4. Interim Analysis

An interim analysis may be conducted for internal decision making. Unblinding details would be specified in the unblinding plan section of the SAP or in a separate unblinding document. The SAP will describe any interim analyses in greater detail should they occur.

9.5. Sample Size Determination

Up to approximately 150 participants will be randomized in a CCI ratio to LY3526318 and placebo, respectively. It is expected that approximately 85% participants will complete the double-blind treatment period of the study. CCI

If there is no treatment difference between placebo and LY3526318, the probability of passing the efficacy criterion specified above (i.e., false positive) is less than 0.05. The simulation for the power calculation and sample size determination was carried out in FACTS Version 6.0.

10. Supporting Documentation and Operational Considerations

10.1. Appendix 1: Clinical Laboratory Tests

The CPMP Master Protocol describes tests that may be performed at additional times noted in the SoA for this ISA. This table describes tests unique for ISA BP02.

Other Tests
LY3526318 concentration
Urine pregnancy

10.2. Appendix 2: Contraceptive and Barrier Guidance

10.2.1. Definitions

Word/Phrase	Definition
Women of childbearing potential	
Females are considered women of childbearing potential (WOCBP) if
 
 • they have had at least 1 cycle of menses, or • they have Tanner 4 breast development. 
Any amount of spotting should be considered menarche. If Tanner Staging of breasts is performed as part of study procedures, please refer to the Reproductive, Pregnancy and Pediatrics Safety Committee Safety Guidance for Children in Clinical Trial regarding Tanner staging.

Women not of childbearing potential	
Females are considered women not of childbearing potential (WNOCBP) if
 
 • they have a congenital anomaly such as Mullerian agenesis • they are infertile due to surgical sterilization, or • they are post-menopausal. 
Examples of surgical sterilization include: hysterectomy, bilateral oophorectomy, or tubal ligation.

Postmenopausal state	
The post-menopausal state should be defined as:
 
 1. A woman at any age at least 6 weeks post-surgical bilateral oophorectomy with or without hysterectomy, confirmed by operative note; or 2. A woman at least 40 years of age and up to 55 years old with an intact uterus, not on hormone therapy*, who has had cessation of menses for at least 12 consecutive months without an alternative medical cause, AND with a follicle-stimulating hormone >40 mIU/mL; or 3. A woman 55 or older not on hormone therapy, who has had at least 12 months of spontaneous amenorrhea, or 4. A woman at least 55 years of age with a diagnosis of menopause prior to starting hormone replacement therapy. 
*Women should not be taking medications during amenorrhea, such as oral contraceptives, hormones, gonadotropin-releasing hormone, anti-estrogens, selective estrogen receptor modulators (SERMs), or chemotherapy that could induce transient amenorrhea.

Reproductive Toxicology Studies	
Embryo-fetal studies are toxicity studies in pregnant animals designed to identify abnormalities in the development of fetuses, which could indicate potential for teratogenicity in humans. The relevant dosing period is during organogenesis.

10.2.2. Contraception Guidance

WOCBP who are completely abstinent as their preferred and usual lifestyle, or in a same-sex relationship, as part of their preferred and usual lifestyle

Must...	Must not...
agree to either remain abstinent, or	
 • use periodic abstinence methods 
 ○ calendar ○ ovulation ○ symptothermal, or ○ post-ovulation • declare abstinence just for the duration of a trial, or
stay in a same-sex relationship without sexual relationships with males	use the withdrawal method

WOCBP who are NOT completely abstinent as their preferred and usual lifestyle, or in a same-sex relationship, as part of their preferred and usual lifestyle

Topic	Condition
Pregnancy testing	Negative urine result at screening followed by a negative serum result within 24 hours prior to treatment exposure. Note: Subsequent pregnancy testing is compound specific.
Contraception	Agree to use 2 forms of effective contraception, where at least 1 form must be highly effective (less than 1% failure rate).

Examples of different forms of contraception

Methods	Examples
Highly effective contraception	
 • combination oral contraceptive pill and mini-pill • implanted contraceptives • injectable contraceptives • contraceptive patch (only women <198 pounds or 90 kg) • total abstinence • vasectomy (if only sexual partner) • fallopian tube implants (if confirmed by hysterosalpingogram) • combined contraceptive vaginal ring, or • intrauterine devices

Effective contraception
	
 • male or female condoms with spermicide • diaphragms with spermicide or cervical sponges • barrier method with use of a spermicide 
 ○ condom with spermicide ○ diaphragm with spermicide, or ○ female condom with spermicide. 
Note: The barrier method must include use of a spermicide (i.e., condom with spermicide, diaphragm with spermicide, and female condom with spermicide) to be considered effective.

Ineffective forms of contraception
	
 • spermicide alone • immunocontraceptives • periodic abstinence • fertility awareness (calendar method, temperature method, combination of above 2, cervical mucus, and symptothermal) • withdrawal • post coital douche, and • lactational amenorrhea

Topic	Guidance

Contraception for men receiving a genotoxic drug and have a female partner of childbearing potential
	
 • Agree to remain abstinent (if this is their preferred and usual lifestyle), or • Use 1 additional effective method of contraception

The table below describes contraception guidance for all men.

Topic	Guidance

For all men
	
should refrain from sperm donation for the duration of the study and for the predicted time until estimated plasma levels of partner would be below the level of toxicologic concern, plus 90 days.

Contraception for men with partners of childbearing potential
	
 • either remain abstinent (if this is their preferred and usual lifestyle), or • must use condoms during intercourse for the duration of the study, and • for the predicted time until estimated plasma levels of partner would be below the level of toxicologic concern, plus 90 days.

Contraception for men in exclusively same-sex relationships, as their preferred and usual lifestyle
	
Are not required to use contraception.

Examples of highly effective, effective, and unacceptable methods of contraception can be found below

Methods	Examples
Highly effective contraception	
 • combination oral contraceptive pill and mini-pill • implanted contraceptives • injectable contraceptives • contraceptive patch (only women <198 pounds or 90 kg) • total abstinence • vasectomy (if only sexual partner) • fallopian tube implants (if confirmed by hysterosalpingogram) • combined contraceptive vaginal ring, or • intrauterine devices
Effective contraception	
 • male or female condoms with spermicide • diaphragms with spermicide or cervical sponges • barrier method with use of a spermicide 
 ○ condom with spermicide ○ diaphragm with spermicide, or ○ female condom with spermicide. 
Note: The barrier method must include use of a spermicide (i.e., condom with spermicide, diaphragm with spermicide, and female condom with spermicide) to be considered effective.

Ineffective forms of contraception	
 • spermicide alone • immunocontraceptives • periodic abstinence • fertility awareness (calendar method, temperature method, combination of above 2, cervical mucus, and symptothermal) • withdrawal • post coital douche, or • lactational amenorrhea.

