5.1. Inclusion Criteria

Participants are eligible to be included in the study only if all of the following criteria apply:

[2050] Are men or women who abide by the reproductive and contraceptive requirements provided in BP02 Section 10.2, Appendix 2.

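### Appendix 2, binding through inclusion criterion [2050], rules out trial-only abstinence in one table but lets it count as a highly effective method in the next

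*Protocol*

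**What the plan says.** Protocol Section 5.1, criterion [2050], admits participants who "Are men or women who abide by the reproductive and contraceptive requirements provided in BP02 Section 10.2, Appendix 2". The appendix is therefore an eligibility rule and not background guidance.

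Section 10.2.2 divides WOCBP into two groups.

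- The first table is headed "WOCBP who are completely abstinent as their preferred and usual lifestyle, or in a same-sex relationship, as part of their preferred and usual lifestyle". Its must-not column includes "declare abstinence just for the duration of a trial, or".
- The second is headed "WOCBP who are NOT completely abstinent as their preferred and usual lifestyle, or in a same-sex relationship" (the heading continues). Its contraception row reads "Agree to use 2 forms of effective contraception, where at least 1 form must be highly effective (less than 1% failure rate". The list of example methods that follows puts "total abstinence" under highly effective contraception, with no condition on lifestyle.

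The same list appears again after the guidance for men. The abstinence options for men do carry the condition that abstinence be their usual way of life. The list entry does not.

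Section 10.2.1 deals with bilateral oophorectomy twice. Under women not of childbearing potential (WNOCBP) it says "Examples of surgical sterilization include: hysterectomy, bilateral oophorectomy, or tubal ligation". Under the postmenopausal state, item 1 is "A woman at any age at least 6 weeks post-surgical bilateral oophorectomy with or without hysterectomy, confirmed by operative note; or".

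**The concern.** A woman who is not usually abstinent and offers abstinence for the length of the study meets two lines that point in different directions. One says she must not do this. The other names it as a highly effective method for her own group. Because [2050] turns the appendix into an entry criterion, two sites could reach opposite eligibility decisions on the same woman.

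The purpose of the criterion is to avoid exposure in pregnancy. The highly effective form carries most of the protection in the two-form rule, so it matters what is allowed to fill that place.

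The oophorectomy lines raise a smaller question. An interval and a documentation requirement were written down, and it is unclear whether they do anything.

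**Working it through.** No figure in the plan is involved, so the check is to read each line as a condition and apply it to test cases.

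**Abstinence.** The rule for WOCBP who are not usually abstinent is: number of forms ≥ 2, and number of highly effective forms ≥ 1. Reading A takes the method list literally, so total abstinence counts as a highly effective form. Reading B applies the ban on trial-only abstinence, so it counts as nothing. Each result is written as forms / highly effective forms.

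| What the woman offers | Reading A | Reading B | Same decision? |
|---|---|---|---|
| Trial-only abstinence alone | 1 / 1, fails | 0 / 0, fails | Yes |
| Trial-only abstinence + condom with spermicide | 2 / 1, meets | 1 / 0, fails | No |
| Trial-only abstinence + intrauterine device | 2 / 2, meets | 1 / 1, fails | No |
| Implant + condom with spermicide | 2 / 1, meets | 2 / 1, meets | Yes |

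The decisions differ when abstinence is one of exactly two forms offered. The second row matters most: under Reading A the only method in use besides the declared abstinence is one that the appendix ranks as effective but not highly effective.

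Could the ban be confined to the table in which it stands? A woman who is abstinent as her settled way of life is not declaring abstinence just for a trial. The ban therefore has content only for a woman outside that heading, and she is the woman the second table covers. The condition attached to abstinence in the men's guidance also shows that the appendix distinguishes settled from newly adopted abstinence. The method list omits that distinction.

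**Bilateral oophorectomy.** WNOCBP status has three routes joined by *or*: congenital anomaly, surgical sterilization, postmenopausal state. Take a woman less than 6 weeks after surgery, or without an operative note, who meets no other route:

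- congenital anomaly: false
- surgical sterilization (bilateral oophorectomy is a listed example, with no interval and no note): true
- postmenopausal item 1: false
- WNOCBP = false OR true OR false = true

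She is WNOCBP whether or not she meets item 1. For this classification the 6-week and operative-note conditions are inert.

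**The case against.** The best defence is that the ban controls entry to the first table. It stops a woman from using trial-only abstinence to escape the two-form rule. If she is not usually abstinent she goes to the second table, where she needs two forms in any case, and the list there is a generic set of examples reused for men. On this view the two tables fit together.

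Part of this stands. The two-form rule does limit the consequence: a reader might infer that a woman could enter on trial-only abstinence alone, and the table above shows she cannot. But the defence does not explain why abstinence that the first table refuses should then fill the highly effective place in the second. It offers one possible reading; the text does not settle on it.

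A reader might also infer that the conflict changes who is tested for pregnancy. The documents do not support this. Both tables concern WOCBP, a woman who is not usually abstinent stays in the second group on either reading, and the Schedule of Activities assigns urine pregnancy tests to all WOCBP. The exclusion of pregnant or breastfeeding women ([2053]) applies independently.

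A further tempting inference is that the oophorectomy lines contradict each other. They do not. Because the routes are alternatives, failing item 1 takes away nothing that the sterilization route grants.

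Finally, the Master Protocol, the disease-state appendix and the Manual of Operations are not among the documents and may hold clarifying text. That is possible, but [2050] points specifically to Appendix 2 of this protocol.

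**Conclusion.** The point holds for abstinence. A binding eligibility appendix forbids trial-only abstinence in one place and counts unqualified abstinence as highly effective in another, for women in whom it can only be newly adopted. Sites can decide differently when abstinence is offered as one of exactly two forms.

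The size is small. About 150 participants are planned, and the documents do not say how many will be WOCBP or what methods they will use, so the number affected cannot be derived. Sample size, error rates and the primary analysis are untouched.

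The oophorectomy point is secondary: a condition without effect, not a contradiction. A site that treats item 1 as the specific rule would apply the interval and the note; a site that uses the sterilization route would not.

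The conclusion assumes that no document outside those reviewed qualifies the abstinence entry. It takes no view on which condition is clinically right.

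**What to change.** 1. Reconcile the "total abstinence" entry with the ban on trial-only abstinence, in both places where the method list appears in Section 10.2.2, so that a woman who is not usually abstinent meets one rule.
2. State the conditions for bilateral oophorectomy once in Section 10.2.1, so that any interval or documentation requirement either governs the classification or is not there.

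The sponsor's safety group should decide which condition stands in each case. The cost is a few lines of wording in one appendix, made in the next amendment or clarified to sites by letter.

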10.3. Appendix 3: List of Excluded Concomitant Medications

10.4. Appendix 4: Provisions for Changes in Study Conduct During Exceptional Circumstances

Implementation of this appendix

The changes to procedures described in this appendix are temporary measures intended to be used only during specific time periods as directed by the sponsor in partnership with the investigator.

Exceptional circumstances

Exceptional circumstances are rare events that may cause disruptions to the conduct of the study. Examples include pandemics or natural disasters. These disruptions may limit the ability of the investigators, participants, or both to attend on-site visits or to conduct planned study procedures.

Implementing changes under exceptional circumstances

In an exceptional circumstance, after receiving the sponsor's written approval, sites may implement changes if permitted by local regulations.

After approval by local Ethical Review Boards, regulatory bodies, and any other relevant local authorities, implementation of these exceptional circumstance changes will not typically require additional notification to these groups, unless they have specific requirements in which notification is required (for example, upon implementation and suspension of changes). All approvals and notifications must be retained in the study records.

If the sponsor grants written approval for changes in study conduct, the sponsor will also provide additional written guidance, if needed.

Considerations for making a change

The prevailing consideration for making a change is ensuring the safety of study participants. Additional important considerations for making a change are compliance with Good Clinical Practice, enabling participants to continue safely in the study and maintaining the integrity of the study.

Informed consent

Additional consent from the participant will be obtained, if required, for:

- participation in remote visits, as defined in Section "Remote Visits,"
- dispensation of additional study intervention during an extended treatment period,
- alternate delivery of study intervention and ancillary supplies, and
- provision of their personal or medical information required prior to implementation of these activities.

Changes in study conduct during exceptional circumstances

Changes in study conduct not described in this appendix, or not consistent with applicable local regulations, are not allowed.

The following changes in study conduct will not be considered protocol deviations.

Remote visits

Telemedicine: Telephone or technology-assisted virtual visits, or both, are acceptable to complete appropriate assessments.

Mobile healthcare: Healthcare visits may be performed by a mobile healthcare provider at locations other than the study site when participants cannot travel to the site due to an exceptional circumstance if written approval is provided by the sponsor.

Procedures performed at such visits include, but are not limited to, collection of blood samples, symptom directed physical examinations, ECGs, vital signs, intervention accountability and compliance, AE collection, and collection of health information.

Other alternative locations: Laboratory draws may be done at an alternate location in exceptional circumstances.

In source documents and the CRF, the study site should capture the visit method, with a specific explanation for any data missing because of missed in-person site visits.

Regardless of the type of remote visits implemented, the protocol requirements regarding the reporting of AEs, SAEs, and product complaints remain unchanged.

Every effort should be made to enable participants to return to on-site visits as soon as reasonably possible, while ensuring the safety of both the participants and the site staff.

Local laboratory testing option

Local laboratory testing may be conducted in lieu of central laboratory testing. The local laboratory must be qualified in accordance with applicable local regulations.

CCI

Study intervention and ancillary supplies (including participant diaries)

When a participant is unable to go to the site to receive study supplies during normal on-site visits, the site should work with the sponsor to determine appropriate actions. These actions may include:

- asking the participant to go to the site and receive study supplies from site staff without completion of a full study visit,
- asking the participant's designee to go to the site and receive study supplies on a participant's behalf, and
- arranging delivery of study supplies.

These requirements must be met before action is taken:

- Alternate delivery of study intervention should be performed in a manner that does not compromise treatment blinding and ensures product integrity. The existing protocol requirements for product accountability remain unchanged, including verification of participant's receipt of study supplies.
- When delivering supplies to a location other than the study site (for example, participant's home), the investigator, sponsor, or both should ensure oversight of the shipping process to ensure accountability and product quality (that is, storage conditions maintained and intact packaging upon receipt).
- Instructions may be provided to the participant or designee on the final disposition of any unused or completed study supplies.

Adjustments to visit windows

Whenever possible and safe to do so, as determined by the investigator's discretion, participants should complete the usual Schedule of Activities as described in the CPMP Master Protocol, CPMP(2) DSA, and BP02 ISA. To maximize the possibility that these visits can be conducted as on-site visits, the windows for visits may be adjusted, upon further guidance from the sponsor. This minimizes missing data and preserves the intended conduct of the study.

For participants whose visits have extended windows, additional study intervention may need to be provided to avoid interruption and maintain overall integrity of the study.

Documentation

Sites will identify and document the details of how participants, visit types, and conducted activities were affected by exceptional circumstances. Dispensing/shipment records of study intervention and relevant communications, including delegation, should be filed with site study records.

Source documents generated at a location other than the study site should be part of the investigator's source documentation and should be transferred to the site in a secure and timely manner.

